7.4 Additional Exploratory Analyses

7.4.1 Physiologically-Based Pharmacokinetic Modeling

Plasma and urine NDMA, DMA, and ranitidine concentration data may be used to conduct physiologically-based pharmacokinetic modeling to better understand absorption, distribution, metabolism, and elimination of these compounds. These analyses will be described in more detail in a separate analysis plan.

7.4.2 Urine and Plasma Metabolomics

Profiling metabolites and other molecular constituents in biofluids may have utility for exploratory research. Portions of collected blood and urine samples from this study may be used for the generation of such profiles (e.g., metabolomics) as hypothesis-generating analyses. Other exploratory analyses may also be performed. Additional details regarding the statistical methods for the exploratory analyses will be described in a separate protocol.

7.4.3 Assessment of Meals

All meals prepared for subjects in this study will utilize foods shown in the literature to have low nitrite/NDMA or high nitrite/NDMA content. However, the actual content of nitrites/NDMA in the different meals will not be known at the time of the study. Two servings of each low nitrite/NDMA meal and each high nitrate/NDMA meal from both a washout and treatment day will be frozen to enable potential analysis of nitrite, NDMA and nitrate content. These results would be summarized as listings (i.e., washout/treatment, high/low, breakfast/lunch/dinner/snack) to document the actual intake of nitrites, NDMA, and nitrates in the different meals.

7.5 Safety Analyses

7.5.1 Adverse Events

All adverse events (AEs) will be coded using the latest version of the Medical Dictionary for Regulatory Activities (MedDRA). The incidence of treatment-emergent adverse event (TEAEs), organized by system organ class and frequency, will be summarized by seriousness, severity, relationship to treatment, and by treatment at onset of the TEAE. A detailed listing of serious AEs and TEAEs leading to withdrawal will also be provided.

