#### **4.6.4.2 Treatment**

The following procedures and assessments will be performed during the treatment period according to the Schedules of Events (Table 8-1):

- Monitor for AEs
- Record concomitant medications
- Measure vital signs (blood pressure, heart rate, respiratory rate, and oral body temperature)
- Administer study drug according to the randomization schedule following all other pre-dose examinations and specimen collection
- Insert IV catheter for blood sampling (if necessary)
- Collect blood samples (8 mL for each sample)
- Collect a urine sample in a specimen collection container. Record weight of the entire sample and collect up to 120 mL of the sample for processing

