#### **4.6.5 Discharge (or Early Termination)**

The following procedures and assessments will be performed before the subject is discharged from the study (Day 8) or at early termination according to Table 8-1:

- Perform a serum pregnancy test (female subjects only)
- Record concomitant medications
- Monitor for AEs
- Perform clinical laboratory tests (hematology, serum chemistry, and urinalysis)
- Measure vital signs (blood pressure, heart rate, respiratory rate, and oral body temperature)
- Perform a safety 12-lead ECG
- Perform a complete physical examination

- Measure height, weight, and calculate body mass index
- Perform alcohol and drug screening (amphetamines, barbiturates, benzodiazepines, cannabinoids, cocaine, alcohol, opiates, phencyclidine, propoxyphene, and methadone)
- Collect a single blood sample (8 mL)
- Collect a urine sample in a specimen collection container. Record weight of the entire sample and collect up to 120 mL of the sample for processing
- Remove IV catheter (if applicable)
- Discharge subject from the study clinic after completion of all study procedures

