##### **4.7.3.1 Adverse Events**

###### **4.7.3.1.1 Adverse Event Definitions**

An AE is defined as any untoward and/or unintended sign, including an abnormal clinical laboratory finding, symptom, or disease temporally associated with the use of a study drug, whether or not considered related to the study drug. Events or conditions that increase in frequency or severity during or as a consequence of use of a drug in human clinical trials will also be considered AEs.

A treatment-emergent adverse event (TEAE) is defined as an AE that begins after study drug administration.

An unexpected AE is any AE having a specificity or severity not consistent with the current investigator's brochure for the study drug(s).

A serious adverse event (SAE) is defined as any AE occurring at any dose that meets the following criteria:

- Results in death,
- Is life threatening,
- Requires hospitalization or prolongation of existing hospitalization,
- Results in persistent or significant disability or incapacity,
- Results in a congenital anomaly/birth defect due to exposure prior to conception or during pregnancy, or
- Is an important medical event that may not meet the previous criteria but, based upon appropriate medical judgment, jeopardizes the subject or requires medical or surgical intervention to prevent one of the outcomes listed previously.

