#### **4.9.8 Safety Analyses**

##### **4.9.8.1 Adverse Events**

All AEs will be coded using the latest version of the Medical Dictionary for Regulatory Activities. The incidence of TEAEs, organized by system organ class and frequency, will be summarized by seriousness, severity, relationship to treatment, and by treatment at onset of the TEAE. A detailed listing of serious AEs and TEAEs leading to withdrawal will also be provided.

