7.5.2 Clinical Laboratory Tests

Clinical laboratory results (hematology, serum chemistry, and urinalysis) will be summarized using descriptive statistics (number of subjects, mean, SD, minimum, median, and maximum). Clinical laboratory results will be classified as normal or abnormal, according to the reference ranges of the individual parameter. The number and percentage of subjects with abnormal laboratory results will be provided. No statistical testing will be performed on clinical laboratory data.

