7.5.4 Safety 12-lead Electrocardiograms

Abnormal 12-lead ECG findings will be recorded as AEs (not planned for each treatment period) in a data listing.

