7.5.5 Physical Examinations

Abnormal physical examination findings will be recorded as AEs (not planned for each treatment period).

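### Scheduled labs come only once after dosing, so discharge-detected TEAEs in completers can fall only under C or D if dated to detection, and no change from Day -2 is planned

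*SAP*

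**What the plan says.** **TEAE table.** SAP 7.5.1 states that TEAEs "will be summarized by seriousness, severity, relationship to treatment, and by treatment at onset of the TEAE"; Protocol 4.9.8.1 matches it. Protocol 4.7.3.1.1 defines a TEAE as an AE beginning after dosing, and its AE definition covers any untoward sign, "including an abnormal clinical laboratory finding, symptom, or disease temporally associated with the use of a study drug". Neither document says how to date the onset of an abnormality that a scheduled test finds.

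**When labs are taken.** Haematology, chemistry and urinalysis are listed at screening (Protocol 4.6.3), at check-in on Day -2 (4.6.4.1), and "before the subject is discharged from the study (Day 8) or at early termination" (4.6.5). The treatment-period list (4.6.4.2) has AE monitoring, vital signs, dosing and PK sampling, but no clinical labs.

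**Lab tables.** SAP 7.5.2 plans descriptive statistics, a normal/abnormal classification against reference ranges, and this count: "The number and percentage of subjects with abnormal laboratory results will be provided". It mentions no visit, change from baseline, direction of abnormality or shift. SAP 7.5.3 does plan changes from baseline for vital signs, split by treatment and time.

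**ECG and physical examination.** SAP 7.5.4 says: "Abnormal 12-lead ECG findings will be recorded as AEs (not planned for each treatment period) in a data listing". SAP 7.5.5 makes the same remark about physical examinations. SAP 7.5.1 does not say how such end-of-study findings enter the by-treatment table.

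**The concern.** A table by treatment at onset invites comparison across A, B, C and D. That comparison means something only if each treatment had a chance to show the event. For abnormalities found by scheduled labs, only the last treatment before discharge has that chance.

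Two things follow. A completer's discharge-lab finding cannot appear under the low nitrite/NDMA treatments, so empty A and B cells could be read as evidence when they only reflect the schedule. And a ranitidine effect that outlasts the next period can be labelled placebo, because every completer has had ranitidine twice by Day 8. The protocol's own risk summary (4.1.2) names effects that labs would detect, including low blood counts and small creatinine rises.

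The lab tables are where a reader would look for a cleaner view. Inclusion criterion 3 (Protocol 4.2.1) admits subjects whose lab abnormalities are judged not clinically significant. A count of subjects with abnormal results therefore cannot separate those who arrived with the abnormality from those who developed it.

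**Working it through.** The plan states no figure on this point, so there is none to reproduce. The check counts which treatment comes last before the Day 8 draw.

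**Inputs.** Sequences ABCD, ABDC, BACD and BADC; the first 16 subjects in blocks of 4, the other two placed in two of the four sequences (SAP 9.1). Doses on Days 1, 3, 5 and 7 (Protocol 4.1.1). Discharge on the morning of Day 8 (Protocol 4.1). All 18 are assumed to complete, with no replacements.

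| Sequence | Subjects | Last treatment | Last ranitidine dose | Approx. time to Day 8 draw |
|---|---|---|---|---|
| ABCD | 4 or 5 | D (placebo) | Day 5 | 72 h |
| BACD | 4 or 5 | D (placebo) | Day 5 | 72 h |
| ABDC | 4 or 5 | C (ranitidine) | Day 7 | 24 h |
| BADC | 4 or 5 | C (ranitidine) | Day 7 | 24 h |

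**Ending on each treatment.** Sixteen subjects in blocks of 4 give 4 per sequence, so 8 end on D and 8 on C. The last two subjects can be placed in six pairs of sequences: one pair adds 2 to D, one adds 2 to C, and four add 1 to each. So 8, 9 or 10 of 18 end on D, with probability 1/6, 4/6 and 1/6; that is 8/18 = 44% to 10/18 = 56%. The rest end on C. None ends on A or B under any placement.

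**Attribution.** If onset is dated to detection, a completer's abnormality first seen at the discharge draw begins after the Period 4 dose and is counted under C or D, whichever period it truly arose in.

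**How much could be labelled placebo.** Let f be the fraction of ranitidine changes visible at 24 h that are still visible at 72 h. The documents do not give f, so the range is shown. With nine subjects ending on each treatment, the expected placebo share of findings from the last ranitidine dose is 9f/(9 + 9f) = f/(1 + f):

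- f = 1: 1/2 = 50%
- f = 0.5: 0.5/1.5 = 33%
- f = 0: 0%

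So misattribution to placebo runs from none, for purely acute effects, to about half, for lasting ones.

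**Lab tables.** SAP 7.5.2 and Protocol 4.9.8.2 set against SAP 7.5.3: the vital-sign section has a baseline comparison and the lab sections have none, although Day -2 and discharge values both exist for each completer.

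**The case against.** The strongest reply is that the dating rule has been supplied from outside. The plan leaves onset to the investigator, who could in principle place it earlier. This stands: the C-or-D restriction depends on dating to detection and must be stated as conditional. But with no lab between Day -2 and discharge, the investigator would usually have nothing on which to base an earlier date, and a blinded relatedness rating does not supply one. A dated symptom or an unscheduled repeat test (Protocol 4.7.3.2 allows repeats) would, and such events are outside this point.

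Second, the schedule table (Protocol Table 8-1) is too damaged in the available text to confirm the absence of labs during treatment. This also stands; the point rests on the procedure lists alone.

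Third, all data go into listings (SAP 7), so with 18 subjects a reader could compare Day -2 and Day 8 values by eye. True, but the summary tables would still carry the ambiguity, and the remedy uses the same data.

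Fourth, C versus D in Period 4 is randomised and nearly balanced. For acute effects, attribution to the last treatment is mostly right. A reader might infer that discharge findings should be moved out of A to D as unassignable. The documents do not support going that far, because it would discard a valid randomised contrast, including a true 24-hour ranitidine signal under C.

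**Conclusion.** The point holds as a minor, cheaply repaired reporting weakness. In completers, and if onset is dated to detection, TEAEs first found by the scheduled discharge lab have structural zeros under A and B. Between 44% and 56% of completers have placebo as the treatment to which such a finding is assigned. The lab section offers no baseline comparison to set beside this. An early terminator's finding would go to the last treatment received, which could be A or B.

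Three stronger readings are tempting and unsupported:

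- **That the table is biased for or against ranitidine.** C versus D stays randomised, and the two leftover subjects are as likely to favour one as the other. A lasting effect blurs the contrast; it creates no one-way bias.
- **That the table will show an excess with high nitrite/NDMA meals.** This needs at least one discharge-lab TEAE, and there may be none. Meal type is in any case tied to period by design.
- **That the trial's conclusions are at risk.** The primary endpoint is untouched, safety is not a stated objective, and no testing of lab data is planned.

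**What to change.** SAP wording only.

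1. **SAP 7.5.2.** Tabulate labs by visit, with change from the last pre-dose value to discharge, and add an overall low/normal/high shift table not split by treatment. State that this contrast is uncontrolled: in completers it follows all four periods and 13 samples × 8 mL × 4 periods = 416 mL of PK blood sampling.
2. **SAP 7.5.1.** Keep attribution to the last treatment. Flag or sub-total TEAEs first found at scheduled discharge tests (lab, ECG or physical examination), and also show them in the overall total. Footnote that in completers A and B cannot contribute such events, and that D may include effects of earlier ranitidine.

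The cost is one extra table and a footnote, from data already collected, with no new samples or visits. The by-treatment summary in Protocol 4.9.8.1 is kept, so the protocol can stand. SAP section 2 allows changes until database lock; a later change would be documented and justified in the study report.

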7.5.2 Clinical Laboratory Tests

Clinical laboratory results (hematology, serum chemistry, and urinalysis) will be summarized using descriptive statistics (number of subjects, mean, SD, minimum, median, and maximum). Clinical laboratory results will be classified as normal or abnormal, according to the reference ranges of the individual parameter. The number and percentage of subjects with abnormal laboratory results will be provided. No statistical testing will be performed on clinical laboratory data.

7.5.3 Vital Sign Measurements

Vital sign measurements and changes from baseline will be summarized using descriptive statistics (number of subjects, mean, SD, minimum, median, and maximum) by treatment and time point.

7.5.4 Safety 12-lead Electrocardiograms

Abnormal 12-lead ECG findings will be recorded as AEs (not planned for each treatment period) in a data listing.

7.5.5 Physical Examinations

Abnormal physical examination findings will be recorded as AEs (not planned for each treatment period).

7.5.6 Other Safety Data

All concomitant medication usage and medications that changed in daily dose, frequency, or both since the subject provided informed consent will be summarized for each subject.

8. Data Quality Assurance

Completed electronic case report forms (eCRFs) are required for each subject randomly assigned to treatment. Electronic data entry will be accomplished through the ClinSpark® remote electronic data capture system, which allows for on-site data entry and data management. This system provides immediate, direct data transfer to the database, as well as immediate detection of discrepancies, enabling site coordinators to resolve and manage discrepancies in a timely

manner. Each person involved with the study will have an individual identification code and password that allows for record traceability. Thus, the system, and subsequently any investigative reviews, can identify coordinators, investigators, and individuals who have entered or modified records.

Furthermore, the investigator retains full responsibility for the accuracy and authenticity of all data entered into the electronic data capture system. The completed dataset and their associated files are the sole property of the sponsor and should not be made available in any form to third parties, except for appropriate governmental health or regulatory authorities, without written permission of the sponsor.

9. Appendices

9.1 Randomization schedule

This is a 4-period, double-blind, crossover study where approximately 18 subjects will be enrolled to receive either ranitidine or placebo administered with meals from a pre-specified menu with foods that are either low or high in nitrites and NDMA. Subjects will be randomized to one of four treatment sequences (i.e., ABCD, ABDC, BACD, or BADC), where treatment codes are summarized in the table below. The sequence randomization is set so that all subjects will be provided low nitrite/NDMA meals for the first two periods of the study and high nitrite/NDMA meals for the last two periods of the study. The first 16 subjects to get enrolled will be randomized in blocks of 4. The remaining two subjects will be randomly placed in 2 of the 4 treatment sequences. The study plans for 1:1 enrollment of males and females, but the randomization will not account for sex and treatment sequence interactions.

Table 3: Treatment Codes and Treatment Names

Treatment Code	Treatment Name
A	Ranitidine (300 mg) + low nitrite/NDMA meals
B	Placebo + low nitrite/NDMA meals
C	Ranitidine (300 mg) + high nitrite/NDMA meals
D	Placebo + high nitrite/NDMA meals

10. References

Zeng T and Mitch WA. 'Oral intake of ranitidine increases urinary excretion of N-nitrosodimethylamine' *Carcinogenesis* 2016 Jun; 37(6): 625-34
